5.3. Visit Window

The final visit of the parent trial should serve as the first visit (Visit 1) of the extension trial and data collected in the parent trial before the first study treatment will serve as baseline data for the extension trial. After Visit 1, subsequent visits will occur 5 days (± 1 day) post-dose at Week 13 (± 2 weeks) and then every 13 weeks (± 2 weeks) ongoing.

Post-baseline unscheduled visit (occurred after the date of initiation of the first dose) or end of study visit (early termination visit) will be mapped to the post-baseline scheduled visit with the closest target study day for each scheduled assessment according to Table 2. If the unscheduled visit is in the middle of two scheduled visits, map it to the later one. After mapping, if there are more than one visit in the same window, the visit closer to the target assessment day will be used. If more than one visit has the equal distance to the target day then the later one will be used, if more than one visit on the same day, use the time or the sequence number to select the later record. For listings and shift tables, all data points will be included.

Table 2. Analysis Window

VISIT	Week	Target Study Day	Study Day Window
Visit 1	Week 1	1	≤ 1
Visit 2	Week 13	90	2, 135
Visit 3	Week 26	181	136, 226
Visit 4	Week 39	272	227, 317
Visit 5	Week 52	363	318, 408
Visit 6	Week 65	454	409, 499
Visit 7	Week 78	545	500, 590
Visit 8	Week 91	636	591, 681
Visit 9	Week 104	727	682, 772
Visit x	Every 13 Weeks $13(x-1)$	$7*13*(x-1)-1$ if $x > 1$	Floor ($7*13*(x-1.5)$), Floor ($7*13*(x-0.5)$)-1

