9.6.2. Stopping/Dose Reductions

The investigator or Medical Expert (and, if needed, with the ISC review) may stop or reduce the dose of investigational product for an individual subject at any time during the trial (please notify the Medical Expert as soon as possible). For example, consideration for stopping or reducing the dose may occur in the presence of the following symptoms and laboratory abnormalities:

- Severe hGH-related AEs at any time during the trial (eg, peripheral edema, severe headache, intracranial hypertension or other adverse drug reaction and/or abnormal laboratory values).
- Pregnancy: A subject must be discontinued from the trial if pregnant.
- IGF-1 > +2.0 SDS: The TransCon hGH dose may be decreased by approximately 20% to the next lower weight bracket, unless a different target SDS is identified in consultation with the Medical Expert. See Section 9.3 for details. (Although the prior *requirement* has been eliminated for a second [“confirmatory”] IGF-1 SDS test prior to dose titration, a second IGF-1 SDS test collected 5 days post-dose (± 1 day) remains optional at the investigator’s discretion.)

Any re-establishment of the prior dose due to a subsequent sub-optimal IGF-1 response should receive prior approval by the Medical Expert.

- In those subjects who have historically been dose titrated to a bracket different than expected for weight, the investigator may—at study visits—recommend maintenance of the current absolute dose until the visit’s IGF-1 SDS values are available. Once the IGF-1 SDS values are available, the investigator may then select the most appropriate dose volume or DCC presentation.
- Evidence of hypersensitivity to TransCon hGH
- Evidence of clinically significant pre-diabetes or diabetes (HbA1c > 6.2% and an absolute increase of 0.5% from the prior visit HbA1c): Confirmation of HbA1c level is required. Once confirmed, TransCon hGH dose may be decreased to the next lower weight bracket. If appropriate follow-up monitoring shows progressively worsening glucose intolerance, additional TransCon hGH dose adjustments may be appropriate.
- Clinical evidence of BIH based on history and physical exam, including visual changes, headaches, nausea, vomiting, and/or papilledema on funduscopy: TransCon hGH treatment should be discontinued while BIH is clinically managed.

Reinstitution of TransCon hGH treatment, preferably at a lower dose, should receive prior approval by the Medical Expert.

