10.2.3. Unscheduled Visits

Unscheduled visits are those visits that occur between regularly scheduled visits and are performed to assess a previously noted AE, abnormal laboratory value(s), and/or clinical findings. In such cases, the subject/parent/legal guardian/caregiver will be contacted to arrange an unscheduled visit. Only focused assessments (guided by the reason for the visit) will occur at these visits.

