8.4. Clinical Laboratory Evaluations

Descriptive summaries of actual (absolute) values and changes from extension study baseline values if applicable will be presented in the tables for the following by visit for the full analysis set:

- Chemistry: sodium, potassium, calcium, phosphate, chloride, total bilirubin, alkaline phosphatase, lactate dehydrogenase (LDH), aspartate aminotransferase (AST), alanine aminotransferase (ALT), gamma glutamyl transferase (GGT), albumin, total protein, creatinine, urea nitrogen, uric acid, serum iron and transferrin
- Hematology: hemoglobin, leukocytes, differential blood count of leukocytes, platelet count
- Hormone Levels: thyroid status (TSH, fT4, and fT3 levels) and morning cortisol
- Glucose Metabolism: HbA1c.
- Lipid Metabolism: Total cholesterol, triglycerides, HDL and LDL

Laboratory values will also be displayed in the data listings and those that are outside the normal range will be flagged, along with corresponding normal ranges. Any out-of-range values that are identified by the investigator as being clinically significant will be presented in a data listing.

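### SAP 5.3 picks one value per window by calendar distance, so a recheck can replace an abnormal scheduled value and many early-termination values leave the by-visit safety tables, with no planned table to recover them

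*SAP*

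**What the plan says.** SAP 5.3 brings extra visits into the visit structure: "Post-baseline unscheduled visit (occurred after the date of initiation of the first dose) or end of study visit (early termination visit) will be mapped". Each one goes to whichever scheduled visit has the nearest target day. Where records compete, "After mapping, if there are more than one visit in the same window, the visit closer to the target assessment day will be used", and "If more than one visit has the equal distance to the target day then the later one will be used". Whether a record was scheduled, abnormal or the last on treatment does not enter the rule. One exemption follows: "For listings and shift tables, all data points will be included".

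The protocol explains why competing records arise. Unscheduled visits (Protocol 10.2.3) are "performed to assess a previously noted AE, abnormal laboratory value(s), and/or clinical findings". When the HbA1c criterion in Protocol 9.6.2 is met, "Confirmation of HbA1c level is required". A repeat IGF-1 test is optional.

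For laboratory results, SAP 8.4 states: "Descriptive summaries of actual (absolute) values and changes from extension study baseline values if applicable will be presented in the tables". These are by visit. Vital signs (8.5), IGF-1 SDS above 2.0 and above 3.0 (8.3), weight and pubertal status (8.7) and part of the antibody output (8.2) are also by visit. Section 8 names no shift table.

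**The concern.** A record that competes with a scheduled value often exists because that value was abnormal; this is among the stated purposes of an unscheduled visit. If the recheck happens to fall nearer the target day, the abnormal value leaves the summary and the repeat takes its place. A value chosen for being high tends to be lower on repeat, so the tabulated figure can look more normal than the visit was. Separately, an early-termination value that shares a window with the last scheduled visit usually loses to that earlier value.

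Long-term safety is the primary objective, and apart from adverse events it is reported mainly through these by-visit tables. The shift-table exemption would limit the damage if shift tables were planned, but none is.

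**Working it through.** **Reproducing Table 2.** The SAP's general formulas give target day 91(x−1)−1 and window floor(91(x−1.5)) to floor(91(x−0.5))−1. They match every printed target (90, 181, … 727) and the printed windows for Visits 3 to 9, each 91 days long. For Visit 2 the formula gives days 45–135. The table prints 2–135 (134 days), so that window is extended back to Day 2. In each window from Visit 2 on, 45 days lie after the target.

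**Inputs.** Visits every 91 days, ±14 days (SAP 5.3). IGF-1, antibodies and vital signs every 13 weeks; HbA1c, chemistry, haematology, hormones and lipids every 26 weeks; bone age annually (protocol synopsis and Schedule of Events). Assumptions not in the documents: the scheduled visit's deviation u is uniform over whole days from −14 to +14 (29 values), termination is uniform over the days between two scheduled assessments, and the rule is applied separately to each assessment.

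**Recheck r days after a scheduled visit.** The recheck wins if |u+r| ≤ |u|, that is if u ≤ −r/2. It needs an early scheduled visit and r ≤ 28.

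| r (days) | values of u that qualify | share |
|---|---|---|
| 7 | −14 to −4 | 11/29 = 38% |
| 14 | −14 to −7 | 8/29 = 28% |
| 21 | −14 to −11 | 4/29 = 14% |
| 28 | −14 | 1/29 = 3% |
| over 28 | none | 0% |

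Example at Visit 5 (target day 363): a triggering HbA1c on day 353 and a recheck on day 367 are 10 and 4 days from target, so the recheck is tabulated. With the visit on day 365 and the recheck on day 379 (2 and 16 days), the scheduled value stays.

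**Early termination after Visit 2 or later.** Given u, the termination value is dropped on 45−|u| of the days that follow. The mean of |u| is 0 on target, 56/15 = 3.73 for ±7 days and 210/29 = 7.24 for ±14 days. The mean number of days strictly between assessments is 90, 181 or 363.

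| Assessment interval | on target | ±7 days | ±14 days |
|---|---|---|---|
| 13 weeks | 45/90 = 50% | 41.27/90 = 46% | 37.76/90 = 42% |
| 26 weeks | 45/181 = 25% | 41.27/181 = 23% | 37.76/181 = 21% |
| annual | 45/363 = 12% | 41.27/363 = 11% | 37.76/363 = 10% |

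In the 13-weekly case the termination value displaces the scheduled one in a further 0%, 4% (3.73/90) and 8% (7.24/90).

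**Two qualifications.** First, a termination before Visit 2 has no scheduled competitor. Counting these, the 13-weekly share at ±14 days is 3×37.76/363 = 31% over about one year, 7×37.76/727 = 36% over two and 11×37.76/1091 = 38% over three.

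Second, the laboratory share is lower because even-numbered windows hold no scheduled sample. For on-target visits, 91/181 = 50% of termination samples fall there. They are kept, but in a row with no routine values beside them. SAP 5.3 maps assessment by assessment, which could instead mean windows built around laboratory visits only. The laboratory share would then be (90.5−7.24)/182 = 46% at ±14 days, or 90.5/182 = 50% on target.

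**The case against.** Nearest-to-target windowing is pre-specified, blind to the value, and a common convention. Under the stated assumptions the scheduled value survives in 62%, 72%, 86% and 97% of rechecks at 7, 14, 21 and 28 days. Listings keep every record. SAP 8.4 flags out-of-range results and lists those judged clinically significant, and 8.3 lists high IGF-1 SDS values. Antibody persistence uses all data. Results that meet the adverse event definition reach the adverse event tables.

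Much of this stands: nothing is lost from the report, and the rule taken alone is not an error. It does not close the gap. Listings give no counts. Under Protocol 12.1.3 an out-of-range result may be an adverse event only if it induces a diagnosis, sign or symptom or requires therapy, and IGF-1 values are excluded unless a sign or symptom accompanies them.

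A reader might also infer that selection works in one direction only, or that values taken at exit are those most likely to show harm. The documents support neither. Selection is by distance, and unscheduled visits for adverse events or clinical findings can add abnormal values. The completion reasons in Protocol 10.1 are commercial availability, alternative access to hGH, or treatment no longer being appropriate (including closed epiphyses). Protocol 7.3.1 lists consent withdrawal and loss to follow-up. Exits driven by harm are possible, but nothing shows that they dominate.

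**Conclusion.** The point holds with moderate confidence and is worth correcting. SAP 5.3 allows a recheck within 28 days of an early scheduled visit to replace the abnormal value that prompted it, and it drops a material share of early-termination values. Section 8 plans no summary that brings either back.

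It would be tempting to say that about 4 in 10 early-termination values vanish from every by-visit safety table. That share fits only 13-weekly assessments such as vital signs and IGF-1 SDS, for terminations after Visit 2. HbA1c, chemistry, haematology, lipids, thyroid tests and cortisol are drawn every 26 weeks and lose about half as much under Table 2 windows. Terminations before Visit 2 have no scheduled value to lose to. A completion visit that is itself a scheduled visit, as Protocol 9.6.2 allows for closed epiphyses, creates no second record.

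All shares rest on assumed uniform timing and are conditional on a recheck or termination occurring. Because the documents give no rate for either, the shift in any table cannot be computed.

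**What to change.** In SAP 5.3, state that by-visit summaries use the scheduled-visit record whenever it exists and an unscheduled record only when it does not. State also whether the 26-weekly tests use the Table 2 windows or windows of their own. Report completion and early-termination values in a separate last-on-treatment row.

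In SAP 8.3 to 8.5, add shift tables from baseline to the worst post-baseline value, using all records. For IGF-1 SDS, add the number of subjects with any value above 2.0 and any value above 3.0. These rows follow Protocol 14.1.1, which asks for no confirmation; SAP 3.3.1 still does and should be aligned.

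The cost is SAP wording, some programming and a few extra tables, with no new data. The safety figures may look slightly less favourable. The shift and last-on-treatment tables would serve the primary objective even if the sponsor keeps the nearest-to-target rule.

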11.3. HEIGHT MEASUREMENT

Height should be measured at each visit, preferably by the same auxologist, at approximately the same time of day using a wall-mounted stadiometer (to minimize bias and reduce variability), the accuracy of which has been verified prior to each visit using a validated metallic calibration rod.

Children < 2 years old should be measured in a recumbent position using a length board placed on a flat, stable surface such as a table. Note: despite previous height measurements being performed on a length board, once a subject is 2 years old, the subsequent measurements should be performed on a stadiometer.

For subjects \geq 2 years old, obtain the height measurement on a wall-mounted stadiometer following the general guidance below:

- The subject should not stretch prior to height determination

- The subject should be standing without shoes and socks. Thin foot covers over bare feet may be worn.
- The subject should be wearing only light clothing so that the subject's pose can be observed
- The subject's gaze should be forward and in a horizontal position (Frankfurt plane)
- The subject's heels should be placed together. If the subject has genu valgum (knock-knee), the knees must be in contact with each other and the heels as close to each other as possible
- The subject's heels, buttocks, shoulders, and occiput of the cranium should all be in contact with the stadiometer
- Upward pressure should be applied to the subject's mandibular rami (jaw)
- The subject's shoulders should be relaxed, and pressure applied to the abdomen to reduce lordosis (spine curvature)
- The counterweight head is lowered until it is in contact with the highest part of the subject's head
- The height measurement is read at the horizontal level with the counter to the nearest 0.1 cm
- The subject should step away from the stadiometer and **repeat the previous steps 2 more times**. Repeated determinations must be within 0.5 cm of each other otherwise three new measurements must be performed and recorded.

For subjects < 2 years old, obtain the height measurement on a length board following the general guidance below ([WHO, 2008](#)):

- The subject should be undressed (diaper/underwear is acceptable)
- The parent/legal guardian/caregiver or another individual should place the subject supine on the length board with the subject's head against the fixed headboard, compressing the hair

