5.4. Derived and Computed Variables

Table 3 provides the rules for derived and computed variables which have been initially identified as important for the analysis of the safety or efficacy as appropriate. It is expected that additional variables will be required. The SAP will not be amended for additional variables that are not related to the primary target or key secondary target variables. Any additional derived or computed variables will be identified and documented in the SAS programs that create the analysis files.

The birth date for each subject is collected on the eCRF. To be consistent with all the other TransCon hGH studies, the 15th day of the reported month is used to calculate the age and related scores. In such case, all the height SDS for the subjects will be calculated using 15th as the birth day. The HSDS reported in the eCRF will not be used as it is based on the actual birth date reported by the subject. FMD K&L will utilize the published SAS macro to calculate the height SDS and no independent QC is required for published SAS macro.

Table 3. Parameter Definition

Parameter	Definition
Annualized Height Velocity at visit x (HV) cm/year	$((\text{Height (Visit } x) - \text{Height (Visit } 1)) * 365) / (\text{Date (Visit } x) - \text{Date (Visit } 1))$ 
From the 15-month (65 weeks) visit onwards, the baseline value used for each successive HV calculation was the patient's height at the visit 52 weeks previously, e.g. height at 13 week served as the baseline value to determine HV at the 65 week ('moving 52 weeks HV basis'). If height at visit 52 weeks previously is missing then most recent height prior to the visit will be used.

Height Deviation Standardized Score (HSDS)	Height SDS will be derived using CDC 2000 (United States of America). A standard SAS program is published at: https://www.cdc.gov/nccdphp/dnpao/growthcharts/resources/sas.htm
Change from baseline	The value of each variable at each post-baseline time point minus the baseline score.
Normalized serum IGF-1 SDS	Proportion of subjects with IGF-1 Standard Deviation Score (SDS) of 0 to +2.0. Also derive for -2.0 to +2.0, -1.0 to +2.0.
Parents' Height SDS	$((\text{Parents Height}/M)^L - 1) / (L \times S)$ 
Where M=median, S= generalized coefficient of variation, and L= power in the Box-Cox transformation, the M, S, L values are obtained from the CDC website; Percentile Data Files with LMS Values

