9.1. Annualized HV

Annualized height velocity is calculated based on the rules stated in Section 5.4. Summary tables and listings for HV absolute values at each timepoint by each group and overall will be generated.

9.2. ΔHSDS

Height Standard Deviation Score is derived based on the rules stated in Section 5.4. Summary tables for absolute values and change from baseline at each timepoint by each group and overall will be generated. The listings will also be presented.

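### A child whose only height in the Visit 2 window is an early one gets an annualised Week 13 height velocity, because the SAP sets no minimum interval

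*SAP*

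**What the plan says.** SAP 5.3, Table 2, gives the Visit 2 row as "Visit 2 Week 13 90 2, 135": target Day 90, window Day 2 to Day 135. An unscheduled or end-of-study visit after the first dose "will be mapped to the post-baseline scheduled visit with the closest target study day for each scheduled assessment according to Table 2". Where several visits fall in one window, "After mapping, if there are more than one visit in the same window, the visit closer to the target assessment day will be used".

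SAP 5.4, Table 3, defines "Annualized Height Velocity at visit x (HV) cm/year" as the height at Visit x minus the height at Visit 1, times 365, divided by the days between the two dates. A different starting height applies only from Week 65. No minimum interval is given. Under SAP 9.1, "Summary tables and listings for HV absolute values at each timepoint by each group and overall will be generated".

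Protocol 8.2 asks for an early termination visit with the Visit 5 assessments as applicable, and the Schedule of Events (18.2) includes height at Visit 5. Protocol 10.2.3 limits unscheduled visits to focused assessments chosen by the reason for the visit.

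**The concern.** Closeness to target chooses between records. When there is only one record in the window, it is used however early it is. A child who leaves the trial three weeks after Visit 1 and attends the termination visit has a height that is labelled Week 13 and divided by about 20 days. Over so short a time the height change is small compared with the error in measuring it, so the resulting rate carries almost no information about growth. It would still count as one full observation in the Week 13 mean, SD, minimum and maximum.

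**Working it through.** **1. Reproduce Table 2.** The general row gives target 91(x−1)−1, lower limit floor(91(x−1.5)) and upper limit floor(91(x−0.5))−1. For Visits 3 to 9 all three printed values reproduce; Visit 3, for example, gives 181, 136 and 226. For Visit 2 the target (90) and upper limit (135) reproduce. The lower limit from the formula is floor(45.5) = 45; the table prints 2.

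**2. Which heights reach Week 13 HV.** A height taken between Day 2 and Day 135 maps to Visit 2. It is used only if the child has no height nearer Day 90. That leaves terminations before Visit 2, and a missed Visit 2 where a height happened to be taken earlier.

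**3. Error in one child's HV.** For an error e (cm) in the height difference over d days, the HV error is e × 365/d. When Visit 1 is Day 1, d is the study day minus 1. Protocol 11.3 supplies two reference values for e. One is the 0.1 cm reading resolution. The other is the repeat tolerance, "Repeated determinations must be within 0.5 cm of each other", which applies within a visit and serves here only as an upper scenario.

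| Days between heights | e = 0.1 cm | e = 0.5 cm |
|---|---|---|
| 10 | 3.7 cm/year | 18.3 cm/year |
| 20 | 1.8 | 9.1 |
| 44 (study Day 45) | 0.8 | 4.1 |
| 74 | 0.5 | 2.5 |
| 90 | 0.4 | 2.0 |

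An error of 9 cm/year needs d of at most 0.5 × 365/9 = 20.3 days when e is 0.5 cm, or 0.1 × 365/9 = 4.1 days when e is 0.1 cm.

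**4. Random error.** The documents give no measurement SD. Assume a per-visit SD s of 0.1, 0.2 or 0.3 cm. The HV error SD is √2 × s × 365/d. Over 20 days this is 2.6, 5.2 or 7.7 cm/year, and the probability of an error of 9 cm/year or more in either direction is 0.05%, 8% or 25%. Over 90 days the SD is 0.6, 1.1 or 1.7 cm/year.

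**5. Effect on the summary.** Protocol 5.3 describes CT-301 as about 150 children randomised 2:1, so the former-Genotropin group is at most about 150/3 = 50.

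- One child with a 9.1 cm/year error moves that group's mean by 9.1/50 = 0.18 cm/year. Across 300 subjects the shift is 0.03.
- The same error raises the group's sample variance by 9.125²/50 = 1.7 (cm/year)² on average.
- The value is also likely to become the minimum or maximum.

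**6. A floor that keeps on-schedule visits.** Protocol 10.2 allows Visit 2 as early as 5 (±1) days after the 11th dose. With weekly dosing from Day 1 the 11th dose falls on Day 71, so the earliest compliant visit is Day 75. That is 74 days after a Day 1 height. A visit before Day 1 lengthens the interval. At 74 days a 0.5 cm error gives 0.5 × 365/74 = 2.5 cm/year.

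**The case against.** The case for leaving the plan alone has substance.

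- **Reach.** A reader might infer that any height in the window is annualised. The selection rule says otherwise: a child with an on-schedule Visit 2 is protected.
- **Unscheduled visits.** These might look like a common route, but height is not routine there, so the early termination visit is the main one.
- **Frequency.** Entrants have completed a prior trial on drug, likely non-compliers are excluded, and the protocol lists retention measures. The documents give no count of early leavers, and it is probably small.
- **The 0.5 cm.** This is a within-visit tolerance that triggers remeasurement. It is not a stated error between visits.
- **Consequence.** HV carries no test or decision rule, and the median and listings are also reported. On the assumed SDs of 0.2 to 0.3 cm, measurement noise at 90 days alone gives a standard error of 1.1/√50 to 1.7/√50, or 0.16 to 0.24 cm/year, in a group of 50. A shift of 0.18 is no larger than that.
- **Day 2.** A reader might take the mismatch with the formula as a typing error. It need not be. Nearest-target mapping sends every post-baseline visit from Day 2 to Visit 2, and a bound of 45 would leave Days 2 to 44 unmapped. For laboratory and vital-sign data the wide window is reasonable.

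All of this limits the size of the problem and none of it supplies a minimum interval. The difficulty lies in applying a window suited to point measurements to an annualised rate.

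**Conclusion.** The gap is real and minor. As written, the plan puts an annualised rate from a very short interval into the Week 13 HV table for any child whose only height in the window is an early one. The figure of about 9 cm/year assumes a 0.5 cm error and heights about 20 days apart; at 0.1 cm the same interval gives 1.8. The 0.18 cm/year shift further assumes one such child in a group of about 50.

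The visible damage would be to the Week 13 SD, the minimum and maximum, and the means of small groups. A reader might infer that the trial's conclusions are at risk. The documents do not support that: the primary objective is safety, HV is summarised descriptively, and few children are likely to be affected.

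**What to change.** Add one sentence to SAP 5.4: HV from Visit 1 is computed only when the two heights are at least 74 days apart; otherwise HV is set to missing and the height is listed. Keep the Day 2 bound in Table 2 for laboratory and vital-sign mapping.

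A cut-off of 76 days, from Day 90 minus 14, would be too strict because it would discard compliant visits at 74 and 75 days. Using the formula's Day 45 limit would keep more values but would let a 0.5 cm error reach about 4.1 cm/year. Choosing between 45 and 74 is a judgement; 74 has the merit of following the protocol's own visit schedule.

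The cost is that a few HV values, mostly from early terminations, are missing from the Week 13 summary. The change should be made before those tables are produced, including for any interim analysis under SAP 4.1.
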